2.2 Secondary Objectives

2.2.1 Key Secondary Objectives

1. To compare zavegeptant to placebo on the proportion of subjects alive and off of oxygen at Day 29.
2. To compare zavegeptant to placebo on the proportion of subjects requiring initiation of invasive mechanical ventilation, non-invasive ventilation or use of high flow nasal cannula through Day 29.
3. To compare zavegeptant to placebo on the proportion of subjects admitted into an intensive care unit (ICU) through Day 29.

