3 STUDY ENDPOINTS

3.1 Primary Endpoint

Efficacy will be measured by the difference between treatment groups in the mean 6-point severity rating at Day 15. The severity ratings are:

1. Death
2. Hospitalized, on invasive mechanical ventilation or ECMO
3. Hospitalized, on non-invasive ventilation or high flow oxygen devices
4. Hospitalized, requiring supplemental oxygen
5. Hospitalized, not requiring supplemental oxygen
6. Not hospitalized

Six point severity ratings are from the 6-point ordinal rating scale eCRFs. Deaths through Day 15 from AE/SAE and subject disposition CRFs are also taken into account.

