3.2 Secondary Endpoints

Procedures are from concomitant procedures eCRFs. Deaths are determined from the following eCRFs: 6-point ordinal severity rating scale; AE/SAE; and subject disposition.

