3.2.1 Key Secondary Endpoints

1. Proportion of subjects who have a 6-point severity rating of 5 or 6, are alive, and do not use supplemental oxygen as a procedure at Day 29.
2. Proportion of subjects who have a 6-point severity rating of 2 or 3, or use any ventilation or high-flow nasal cannula as procedures, on any day through Day 29.
3. Proportion of subjects admitted into an ICU on any day through Day 29 from AE/SAE eCRFs.

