3.2.2 Other Secondary Endpoints

1. Number of subjects with deaths, SAEs, severe AEs, and Grade 3 or 4 laboratory test abnormalities at any time on study. All AEs are from AE/SAE eCRFs. Grade 3 or 4 laboratory test abnormalities are determined from laboratory test values graded using standardized criteria defined in the SAP (e.g., CTCAE) from laboratory test eCRFs.
2. Number and percentage of subjects with severe or life-threatening bacterial, invasive fungal, or opportunistic infections at any time through Day 29 from AE/SAE eCRFs.

3. Number and percentage of subjects with intranasal administration reactions at any time through Day 29 from AE/SAE eCRFs.
4. Proportion of subjects with 250% reduction in eGFR from baseline at any time on study from laboratory test eCRFs.

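### Key secondary endpoints 2 and 3 leave death out of the event, so a lower rate on either need not mean benefit

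*Protocol*

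**What the plan says.** The six-point scale in Protocol section 3.1 makes death category 1, the worst. Section 3.2.1 then defines three key secondary endpoints:

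- Endpoint 1 counts subjects who "have a 6-point severity rating of 5 or 6, are alive, and do not use supplemental oxygen as a procedure at Day 29". A death is a failure.
- Endpoint 2, over the period to Day 29, counts those "who have a 6-point severity rating of 2 or 3, or use any ventilation or high-flow nasal cannula as procedures, on any day". Rating 1 is not listed.
- Endpoint 3 is the "Proportion of subjects admitted into an ICU on any day through Day 29 from AE/SAE eCRFs". Death is not mentioned.

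The matching objectives in section 2.2.1 do not mention death either. Objective 2 concerns the "proportion of subjects requiring initiation of invasive mechanical ventilation, non-invasive ventilation or use of high flow nasal cannula through Day 29". Objective 3 is "To compare zavegeptant to placebo on the proportion of subjects admitted into an intensive care unit (ICU) through Day 29".

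The lead-in to section 3.2 states "Deaths are determined from the following eCRFs: 6-point ordinal severity rating scale; AE/SAE; and subject disposition". That names the data sources. It does not make death an event in endpoint 2 or 3.

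Under section 9.3.3 the key secondary endpoints are tested with the Holm procedure if the primary endpoint is significant, on the efficacy set. Section 9.2 defines that set as subjects randomized only once who received at least one dose, so subjects who die remain in it. Some text in section 9.3.3 is redacted; nothing here depends on it.

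**The concern.** Death is a competing event for both endpoints: a subject who dies can no longer be escalated or admitted to an ICU. As written, such a subject is a non-event, which on these endpoints is the good outcome.

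The two endpoints are exposed to different degrees. Endpoint 2 is affected only by deaths that never went beyond ordinary supplemental oxygen. Endpoint 3 is affected by every death without an ICU admission, including deaths on a ward on non-invasive ventilation or high flow.

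Both endpoints are alpha-controlled and meant to support an efficacy claim. If deaths without the event are more frequent on zavegepant, a lower escalation or ICU rate may partly reflect those deaths. If they are more frequent on placebo, a real benefit may be hidden.

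Section 6.5.3 plans to record withdrawal of care and care decisions driven by limited resources. That makes such deaths possible but does not show how many there would be.

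**Working it through.** **Inputs.** Planned arms of 80 and 40 subjects and a family alpha of 0.05 (sections 9.1 and 9.3.3). Three key secondary endpoints (section 3.2.1), so the first Holm step is 0.05/3. The protocol states no rate of escalation, ICU admission or death without either, so every rate below is an assumption.

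**Weight of one death.** A single death without the event lowers the as-written rate by 1/40 = 2.5 points on placebo, or 1/80 = 1.25 points on zavegepant, relative to counting it as an event.

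**Formula.** Let c be the rate of death-or-event and d the rate of death without the event, with subscripts p (placebo) and z (zavegepant). The as-written event rate is c − d, so the apparent benefit is (c_p − d_p) − (c_z − d_z). If d_p = d_z, it equals c_p − c_z and nothing is distorted.

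**Test used.** Exact binomial enumeration over 80 versus 40 subjects, two-sided Fisher exact test at p ≤ 0.05/3. The gate on the primary endpoint is not applied.

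**(a) No true difference: death-or-event 30% in both arms.**

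| d_z / d_p | As-written rate, zavegepant / placebo | Apparent benefit (points) | Favourable result | Unfavourable result |
|---|---|---|---|---|
| 2.5% / 2.5% | 27.5% / 27.5% | 0 | 0.68% | 0.60% |
| 5% / 2.5% | 25% / 27.5% | +2.5 | 1.52% | 0.25% |
| 7.5% / 2.5% | 22.5% / 27.5% | +5 | 3.17% | 0.10% |
| 2.5% / 5% | 27.5% / 25% | −2.5 | 0.29% | 1.27% |
| 2.5% / 7.5% | 27.5% / 22.5% | −5 | 0.11% | 2.57% |

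For comparison, the composite with death (30% versus 30%) gives a favourable result in 0.65%.

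**(b) True benefit: death-or-event 40% on placebo, 20% on zavegepant.** The composite is significant in favour of zavegepant in 43.3%. As written, with d_z = 2.5%:

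| d_p | As-written rate, zavegepant / placebo | Apparent benefit (points) | Favourable result |
|---|---|---|---|
| 2.5% | 17.5% / 37.5% | 20 | 46.2% |
| 5% | 17.5% / 35% | 17.5 | 35.7% |
| 7.5% | 17.5% / 32.5% | 15 | 26.0% |

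**Scale.** At as-written rates of 27.5% on placebo and 22.5% on zavegepant, the standard error of the difference is √(0.275 × 0.725/40 + 0.225 × 0.775/80) = 8.5 points. A 5-point distortion is therefore 5/8.5, about 0.6 standard errors.

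**The case against.** The strongest reply is that nothing is contradicted. Objectives 2 and 3 ask about starting respiratory support and about ICU admission, the endpoints measure exactly that, and a composite with death asks a different question. That is correct: the count is right for the quantity as worded. But agreement between objective and endpoint does not make a lower rate readable as benefit when neither says what happens to subjects who die first.

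The second reply is that death is covered elsewhere. It is the worst score on the gating primary, where "Deaths through Day 15 from AE/SAE and subject disposition CRFs are also taken into account". It is a failure on key secondary endpoint 1 at Day 29. It is also tabulated in section 3.2.2 under "Number of subjects with deaths, SAEs, severe AEs, and Grade 3 or 4 laboratory test abnormalities at any time on study". This limits the risk of a wrong overall conclusion, and a reader can cross-check. It also means that the favourable-result chances in scenario (a) are upper figures: excess zavegepant deaths by Day 15 would push the primary the wrong way and tend to keep the gate closed. Deaths on Days 16 to 29 are not in the gate, however, and the tests of endpoints 2 and 3 ignore deaths without the event whenever they occur.

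The third reply is that such deaths may be rare. Exclusions 7 and 12 in section 5.3 remove subjects with multi-organ failure and those unlikely to survive 48 hours. Withdrawal of care does not mean that care was never escalated. This stands, most strongly for endpoint 2, and the documents cannot settle the frequency.

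Finally, when such deaths are equally frequent the composite has slightly less power than the endpoint as written (43% versus 46%). That is true, and it is a small cost. The SAP, which was not available, may add supportive analyses, but the protocol fixes what counts as an event.

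**Conclusion.** The concern holds. Two of the three Holm-tested key secondary endpoints score a death without escalation, or without ICU admission, the same as a recovery, while the first endpoint in the same list treats death as failure.

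The consequence is conditional on such deaths differing between arms. Under the assumed rates, inflation of false favourable results is small in absolute terms (at most about 3.2% at the first Holm step, before the gate). The clearer cost is masking: with a 5-point placebo excess, power falls to 26%, against 43% for the composite. All these rates are illustrative.

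This is an inexpensive improvement in definition, not a flaw that invalidates the trial.

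**What to change.** In section 3.2.1, define the endpoint 2 event as all-cause death, or any ventilation or high-flow use, through Day 29. Define the endpoint 3 event as all-cause death or ICU admission through Day 29. Take deaths from the sources already named in section 3.2, reword objectives 2 and 3 in section 2.2.1 to match, and report escalation, ICU admission and death separately by arm.

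The cost is the wording of two endpoints and two objectives, with no new data. The drawback is that the endpoints become composites answering a slightly different question, and deaths unrelated to escalation add some noise. That is why the components must be shown.

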3.2.2 Other Secondary Endpoints

1. Number of subjects with deaths, SAEs, severe AEs, and Grade 3 or 4 laboratory test abnormalities at any time on study. All AEs are from AE/SAE eCRFs. Grade 3 or 4 laboratory test abnormalities are determined from laboratory test values graded using standardized criteria defined in the SAP (e.g., CTCAE) from laboratory test eCRFs.
2. Number and percentage of subjects with severe or life-threatening bacterial, invasive fungal, or opportunistic infections at any time through Day 29 from AE/SAE eCRFs.

3. Number and percentage of subjects with intranasal administration reactions at any time through Day 29 from AE/SAE eCRFs.
4. Proportion of subjects with 250% reduction in eGFR from baseline at any time on study from laboratory test eCRFs.

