2.2.2 Other Secondary Objectives

1. To examine the safety of zavegeptant, relative to placebo, as reflected by the number of: deaths; SAEs; severe AEs; and Grade 3 or 4 laboratory test abnormalities.
2. To examine the safety of zavegeptant, relative to placebo, as reflected by the incidence of severe or life-threatening bacterial, invasive fungal, or opportunistic infections through Day 29.
3. To examine the safety of zavegeptant, relative to placebo, as reflected by the incidence of intranasal administration reactions through Day 29.
4. To examine the safety of zavegeptant, relative to placebo, as reflected by the proportion of subjects who develop a significant loss of renal function, defined as at least 50% reduction in eGFR from baseline.

CCI

[REDACTED]

[REDACTED]

[REDACTED]

[REDACTED]

CCI

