5.3 Exclusion Criteria

1. Subjects in immediate need of invasive mechanical ventilation or extracorporeal membrane oxygenation (ECMO).
2. Subjects with an eGFR of < 30 mL/min, at the Screening Visit
3. Prisoners or subjects who are involuntarily incarcerated
4. Subjects who are participating in any other investigational clinical trial while participating in this clinical trial

5. Subjects who are under the age of 18 years
6. Subjects who are pregnant (all potential female enrollees need to have a negative pregnancy test prior to IP administration)
7. Subjects with multi-organ failure
8. Subjects who have received more than 48 hours of supplemental oxygen prior to randomization
9. Subjects with prior significant pulmonary disease (e.g., severe COPD/ILD/CHF/IPF) are excluded
10. Subjects receiving investigational therapies as part of a formal clinical trial for the treatment of COVID-19. During the course of this study, investigational therapies that may become “standard of care” to treat COVID-19, but are not part of a clinical trial, are allowed.
11. Subjects who are on long-acting CGRP monoclonal antibodies will be excluded including Aimovig® (erenumab), Emgality® (galcanezumab), Ajovy® (fremanezumab), and Vyepti® (eptinezumab). Additionally, the investigational oral CGRP receptor antagonist, atogepant, that is taken daily will also be excluded. Oral CGRP receptor antagonists, Nurtec® ODT (rimegepant) and Ubrelvy™ (ubrogepant) that are typically used PRN infrequently will not be excluded as long the subject was not taking them on a daily basis and does not take them during the current study
12. Subjects who are unlikely to survive for more than 48 hours from the Screening Visit
13. Subjects with any of the following abnormal laboratory values at screening: aspartate AST or ALT greater than 5x ULN or bilirubin greater than 2x ULN
14. Subjects with known active TB, history of incompletely treated TB, suspected or known extrapulmonary TB
15. Subjects with suspected or known systemic bacterial or fungal infections. However, empiric antibiotics are permitted
16. Subjects who have participated in any clinical research study evaluating an IP or therapy within 3 months and less than 5 half-lives of IP prior to the screening visit

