9.3.6 Analysis of Safety

The investigators determine the intensity of AEs and the relationship of AEs to study therapy. The investigators' terms are coded and grouped by system organ class using the latest version of the Medical Dictionary for Regulatory Activities (MedDRA) available. AEs are presented by system organ class and preferred term in descending order of overall frequency of events. If a subject had an AE with different intensities over time, then only the greatest intensity is reported.

Deaths, all AEs, and SAEs are listed for the enrolled analysis set.

The frequencies of the following safety events on study are summarized by treatment group and overall for the safety analysis set: SAEs; AEs by intensity and overall; treatment-emergent AEs by intensity and overall; AEs leading to study drug discontinuation; and treatment-emergent AEs by relationship to study drug.

Clinically significant laboratory test abnormalities on study will be identified as Grade 3 to 4 laboratory test results graded according to numeric laboratory test criteria in CTCAE Version 5.0 (2017), if available. Otherwise, if CTCAE grades are not available, then results will be graded

according to numeric laboratory test criteria in Division of AIDS (DAIDS) Table for Grading the Severity of Adult and Pediatric Adverse Events Corrected Version 2.1 (2017). If a subject has a laboratory test abnormality with different toxicity grades over time, then only the highest toxicity grade will be reported.

Further safety analyses will be described in the SAP.

9.3.7 *Futility Analysis*

A formal futility analysis will be performed by the DMC statistician after approximately 50% of subjects complete the 14-day treatment period.

The DMC will test for futility stopping only. This test will not be counted against the alpha spend for the study. In particular, zavegeptant will be tested for inferiority to placebo, on the primary endpoint (the six point, ordinal, severity scale). This will be done using a Wilcoxon rank sum test at a one-sided alpha level of 0.05.

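### The Grade 3–4 laboratory endpoint ignores the pre-dose grade, so abnormalities carried in from entry count as on-study events and blunt the comparison on those tests

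*Protocol*

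**What the plan says.** Other secondary endpoint 1 in Protocol Section 3.2.2 is "Number of subjects with deaths, SAEs, severe AEs, and Grade 3 or 4 laboratory test abnormalities at any time on study". The section leaves the grading criteria to the SAP, naming CTCAE as an example.

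Section 9.3.6 gives the counting rule: "Clinically significant laboratory test abnormalities on study will be identified as Grade 3 to 4 laboratory test results graded according to numeric laboratory test criteria", with CTCAE 5.0 first and the DAIDS table where CTCAE has no grade. It continues: "If a subject has a laboratory test abnormality with different toxicity grades over time, then only the highest toxicity grade will be reported". Section 9.3 adds that repeated occurrences of the same laboratory abnormality count once per subject.

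Two neighbouring measures do look back to baseline. Section 9.3.6 lists "treatment-emergent AEs by intensity and overall" separately from AEs on study. Objective 4 in Section 2.2.2 measures renal loss, "defined as at least 50% reduction in eGFR from baseline".

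At entry, Section 5.3 excludes subjects with "AST or ALT greater than 5x ULN or bilirubin greater than 2x ULN" and those with eGFR below 30 mL/min. It sets no limit on any other test in the safety panel of Section 6.3.5.1.

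**The concern.** A graded laboratory value does not show when the abnormality began. AEs do not have this problem, because Section 8 defines an AE as something new or a worsening of something already there. The laboratory endpoint has no equivalent condition. It asks only whether a Grade 3–4 value was seen on study.

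The subjects are in hospital with COVID-19 and on oxygen, so some abnormal values at entry are plausible. The safety panel is drawn on Days 1, 2, 5, 10, 15, 22 and 29 (Table 1), so an abnormality that has not cleared is measured again soon after the first dose. The same rule applies in both arms and randomization balances entry abnormalities in expectation, so neither arm is favoured. The loss is in contrast: the objective is safety relative to placebo, and events that the drug could not have caused add to both arms in a trial with 40 controls.

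**Working it through.** The protocol states no event rate, count or power for this endpoint, so there is no figure to reproduce. The check has two parts.

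**1. What the wording does to four subjects, for one test**

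| Pre-dose grade | Worst grade after first dose | Event as worded? | New or worse? |
|---|---|---|---|
| 0–2 | 3 or 4 | Yes | Yes |
| 3 | 4 | Yes | Yes |
| 3 | 3 | Yes | No |
| 4 | 3 | Yes | No |

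The last two rows are the problem. The highest-grade rule does not remove them, because it selects among a subject's grades and does not compare them with baseline.

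**2. Direction and illustrative size**

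Inputs from the protocol: 80 subjects on zavegepant and 40 on placebo (Section 4.3.3). Assumed inputs, not in the protocol:
- f, the share of each arm with an entry Grade 3–4 abnormality that persists on study.
- p0 and p1, the new-onset rates on placebo and on drug.
- A single pooled event, meaning any test.

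Counted rate as worded = f + (1 − f)p. Difference = (1 − f)(p1 − p0). Risk ratio = [f + (1 − f)p1] / [f + (1 − f)p0].

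For example, with f = 0.2, p0 = 10% and p1 = 30%:
- Placebo: 0.2 + 0.8 × 0.10 = 28%.
- Drug: 0.2 + 0.8 × 0.30 = 44%.
- Ratio: 44 / 28 = 1.57.

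In expected counts this is 40 × 0.28 = 11.2 placebo events, of which 40 × 0.2 = 8 were present at entry. On drug it is 80 × 0.44 = 35.2, of which 80 × 0.2 = 16 were present at entry.

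| New onset, placebo vs drug | f | Counted, placebo vs drug | Difference (points) | Risk ratio |
|---|---|---|---|---|
| 10% vs 30% | 0 | 10% vs 30% | 20 | 3.00 |
| | 0.1 | 19% vs 37% | 18 | 1.95 |
| | 0.2 | 28% vs 44% | 16 | 1.57 |
| 10% vs 25% | 0 | 10% vs 25% | 15 | 2.50 |
| | 0.1 | 19% vs 32.5% | 13.5 | 1.71 |
| | 0.2 | 28% vs 40% | 12 | 1.43 |
| 20% vs 40% | 0 | 20% vs 40% | 20 | 2.00 |
| | 0.1 | 28% vs 46% | 18 | 1.64 |
| | 0.2 | 36% vs 52% | 16 | 1.44 |

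At the far end, f = 0.5, the three ratios fall to 1.18, 1.14 and 1.17.

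Persistence matters as much as prevalence. If 20% enter with a Grade 3–4 value and half of these persist, f = 0.2 × 0.5 = 0.1, so the ratio in the first scenario is 1.95 and not 1.57.

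The ratio comparison does not depend on how subjects abnormal at entry are treated under a new-or-worse rule. If they can have no new event and stay in the denominator, the rates at f = 0.2 are 0.8 × 10% = 8% and 0.8 × 30% = 24%, a ratio of 3.0. The difference is then 16 points, the same as under the wording. In that case the loss lies in the ratio and in the noise added to both arms.

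**The case against.** **The SAP may settle it.** Section 9 places full statistical detail in the SAP, Section 9.3.6 leaves further safety analyses to it, and baseline handling of graded values is routine SAP content. On study is also undefined. This has weight: the SAP is not shown and may already contain the condition. But Section 3.2.2 defers only the grading criteria. The window and the highest-grade rule are fixed in the protocol, and an additional SAP analysis would not change them.

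**The entry limits work against the point.** A reader might infer from the permitted AST/ALT, bilirubin and eGFR values that subjects enter already at Grade 3–4 on these tests. The protocol does not support that. These limits are exclusions that remove the larger entry abnormalities, and the grade thresholds are not in the document. Moreover, Table 1 schedules liver tests only at screening and Day 15, so an entry liver abnormality would normally have to last about two weeks to be counted. This objection stands, and it confines the point mainly to haematology and other chemistry tests.

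**Dilution of any drug signal would be too broad.** Sections 9.3 and 9.3.6 speak of the same event and of a given abnormality, which suggests tabulation by test. An entry abnormality on one test then leaves another test's comparison untouched. Clinically significant values are also reported as AEs (Sections 6.3.5 and 8.4.2), treatment-emergent AEs are summarised, and renal loss is measured from baseline. This stands too.

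**Deaths, SAEs and severe AEs in the same endpoint are also counted at any time on study.** True, but the AE definition in Section 8 already requires something new or worse. A laboratory grade does not.

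**Power.** With 30% vs 10% new onset and f = 0.2, a two-sided 0.05 comparison of proportions would have power of about 39% as worded, against 57–58% for new events only. A reader might take this as the cost to the trial. The protocol states no test of this endpoint, so these figures only illustrate lost sensitivity.

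**Conclusion.** The point holds in a limited form. As worded, Sections 3.2.2 and 9.3.6 count a Grade 3–4 value that was present at entry and persists, or improves only from Grade 4 to 3, as an on-study event in either arm. This reduces sensitivity on the tests abnormal at entry. A reader might go further and infer bias toward one arm, but the protocol does not support that, since the rule is the same in both arms of a randomized comparison.

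The actual size is unknown. A fall in the risk ratio from 3.0 to about 1.95 to 1.57 rests on assumed new-onset rates of 30% vs 10%, an assumed persisting entry share of 10% to 20%, and pooling of all tests into one event. With by-test tables or entry abnormalities that clear early, the effect would be smaller. This is a minor improvement to a descriptive safety count.

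**What to change.** In Sections 3.2.2 and 9.3.6, define the event per test: a Grade 3 or 4 value after the first dose that is a higher grade than the last grade before the first dose for that test. Add a baseline-to-worst-grade shift table by arm. Keep the maximum grade on study as a supporting listing. Decide pre- or post-dose by sample time, because Section 4.1 starts Visit Day 1 at the first dose and a Day 1 draw could otherwise be read either way.

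The cost is one sentence in each section and one table. No new data are needed, since screening and on-study tests are already scheduled in Table 1. The downside is that a subject already at the top grade for a test cannot have an event on that test. The shift table shows how many such subjects there are.
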